9.1.2 Treatment Compliance

All dispensed drugs are expected to be taken and no calculations of treatment compliance can be done.

10 SAFETY

General considerations

The present study will be based on the secondary use of data that has already been collected for other purposes. Thus, according to the European Medicines Agency (EMA) Good Pharmacovigilance Practices (GVP) Module VI, (EMA, 2017), the submission of suspected adverse reactions in the form of individual case safety reports is not required. All adverse events/reactions collected for the study will be recorded and summarized in the interim analysis and in the final study report. Since it is not required to collect or submit any safety data for the study, reconciliation is not applicable.

Given between-country differences in the type of data used, governance regulations and patient privacy rules, and expected variations in the background risk of diseases, the countries will be analysed separately and combined in a meta-analysis (where the estimates for each country and cohort will be pooled, as applicable). The meta-analysis will be performed only for the final report which is planned in December 2023.

The distribution of continuous variables (age and exposure time) will be examined graphically using boxplots, symmetry plots, normal quantile plots and normal probability plots as shown in Figure 11, Figure 12, Figure 13, and Figure 14. Exploratory analyses to provide insight into general patterns will be conducted using number and percent within each category with 95% confidence interval (CI) for categorical variables except cohort characteristics, and mean (standard deviation, SD), median (interquartile range, IQR), and other relevant summary statistics for continuous variables. Where/if appropriate, a log transformation of continuous variables (age) will be applied to handle skewness (back-transformed prior to reporting) or a non-parametric approach will be adopted if there is no appropriate transformation. Quantitative variables may be categorised into quartiles as required. These possible back-transformation and quartiles presentation will be judged after the report for the first year 2021 has been completed. These distribution figures is an option for BIPS, who can choose not to produce these figures.

Missing data for covariates will be described. Since missing values are expected to be few and distributed at random, in general, no replacement or imputation will be performed. Missing values will not be considered in the denominators for proportions. For many registries, if no information about a condition is given it indicates that the condition has not occurred, e.g. lack about a heart failure before the index date must be interpretation as that a heart failure has not happen.

The statistical analysis will be conducted using the SAS[®] software (version 9.3 or later) on Windows[™] (SAS Institute, North Carolina, US) or using R statistical program (version 3.5.0 or later).

10.1 Primary Safety Endpoint(s)

10.1.1 Primary Analysis

All descriptive analyses outlined below will performed in the Nocdurna \mathbb{R} cohort, the LUTS group, and stratified by subgroups (elderly patients aged ≥ 65 years, patients with and without contraindications) as shown in Table 10. The study objectives are descriptive and no hypothesis have been formulated. Comparative analysis are done in secondary objective 7, as described in section 10.2.8.

10.1.2 Incidence of symptomatic hyponatraemia

The incidence rate of the primary outcome reported since index date in the study period will be modelled using a Poisson regression model and expressed as number of cases per 1000 patientsyears at risk (+- 95% CI) for the Nocdurna ® group and the LUTS contextual cohort, separately. Person-period at risk is defined according to person-time observed from the index date to the first right censoring event. The dependent variable will be number of events for each person and the independent variable will be treatment, age class, and gender. Stratum-specific incidence rates will also be examined giving rates divided by gender, first month after index date and events occurring after the first month after the index date. Also incidence rates for patients with an age above or equal to 65 years will be calculated. If the model does not converge/modelling assumptions are not met, only unadjusted rates will be presented. This gives the following high level table shell.

Table 4. Thgh level of	uipui uesenj		r ofsson regie	551011		
	Nocdurna	R		LUTS		
	All	Male	Female	All patients	Male	Female
	patients					
All events	X (x-x)	X (x-x)	X (x-x)	X (x-x)	X (x-x)	X (x-x)
First month	X (x-x)	X (x-x)	X (x-x)	X (x-x)	X (x-x)	X (x-x)
After first months	X (x-x)	X (x-x)	X (x-x)	X (x-x)	X (x-x)	X (x-x)
≥ 65 y, All events	X (x-x)	X (x-x)	X (x-x)	X (x-x)	X (x-x)	X (x-x)

Table 4. High level output description of the Poisson regression

A complete table is shown in Table 9

A SAS macro for doing the above analysis has been developed and is described and attached in section 16.2 of this report. The analysis of events during the first month will limit the exposure time to a maximum of 30 days, while the analysis of events after the first month will subtract 30 days for the exposure time. However, there will also be patients that are enrolled late in the study e.g. in the month of December and these patients will have an exposure time of less than 30 days. It must be noted that the analysis of events after the first month is having an immortal time bias, but this bias is expected to be small, since (hopefully) very few patients will die or emigrate during the first month.

10.1.3 Sensitivity Analyses

Sensitivity analyses will be performed to assess the robustness of the study findings:

The assumptions underlying the construction of Nocdurna ® treatment episodes will be tested. The length of the permissible gap will be shortened. For overlaps of two subsequent prescriptions, beginning of the second prescription will be shifted to the end of the first reducing the permissible gap to zero days. Table shells for this sensitivity analysis are shown from Table 45 to Table 51. The estimation of prescription duration will also be examined. Instead of estimating prescription duration based on the recommended daily dose of Nocdurna ® (1 oral lyophilisate), the dose actually prescribed to the individual patient will be considered (Sweden, Denmark). This analysis will be subject to availability of data on individual dosage instructions in the database/registry. The

method for this analysis will be the following. All dosing texts will be listed in a frequency table sorted with the most frequent text at the top. This table will be moved to EXCEL and a manual coding of the 98% of the most frequent dosing text will be done. The information will be moved back into SAS and the numeric value of the dosing instruction will be used in the sensitivity analysis as described above. Only the Nocdurna ® patients will have their dosing changed in this way. If the dosing text is informing the patient to use the drug 'as needed/vid behov/as explained or similar' this will be interpreted as 0.5 tablets per day. Often will the dosing text be like this without a specific instruction to the user. Table shells for this sensitivity analysis are shown from Table 52 to Table 58. This analysis is only possible in Sweden where the prescribing text is available.

The first sensitivity with shortened gap is expected to give a lower number of events, and at the same time also reduce the exposure time so the effect on the incidence rate cannot be predicted.

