9.7.3 Sensitivity analyses

Sensitivity analyses will be performed to assess the robustness of the study findings:

 The assumptions underlying the construction of NOCDURNA treatment episodes will be tested. The length of the permissible gap will be varied (shortened or lengthened). For overlaps of two subsequent prescriptions, beginning of the second prescription will be shifted to the end of the first. The estimation of prescription duration will also be examined. Instead of estimating prescription duration based on the recommended daily dose of NOCDURNA (1 oral lyophilisate), the dose actually prescribed to the individual patient will be considered (Sweden, Denmark). This analysis will be subject to availability of data on individual dosage instructions in the database/registry.

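### The prescribed-dose sensitivity analysis sets dosing texts that state no dose to 0.5 tablets per day, so for those dispensations it tests an unsupported constant, not a prescribed dose

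*Protocol*

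**What the plan says.** Protocol section 9.7.3 and SAP section 10.1.3 describe the same sensitivity analysis. Prescription duration will no longer rest on the recommended one lyophilisate per day; instead "the dose actually prescribed to the individual patient will be considered", subject to data availability.

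SAP section 10.1.3 adds the method. Dosing texts are listed by frequency, and "a manual coding of the 98% of the most frequent dosing text will be done". Numeric instructions are used as written. If the text tells the patient to "use the drug 'as needed/vid behov/as explained or similar", then "this will be interpreted as 0.5 tablets per day. Often will the dosing text be like this without a specific instruction to the user". The recoding is one-sided: "Only the Nocdurna ® patients will have their dosing changed in this way". The results go to Tables 52 to 58. The section closes by saying that the run is possible only in Sweden.

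SAP section 9.1.1 defines the permissible gap as equal to the days supplied by the latest dispensation. It therefore scales with whatever daily dose is assumed. The SAP gives no reason for 0.5, no alternative value, no plan to report how many dispensations are affected, and no rule for texts outside the coded 98%. The list of changes in SAP section 13 does not mention the rule.

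**The concern.** The stated purpose is to see whether results hold when the assumed dose is replaced by the prescribed one. The rule puts two kinds of text under one code. *As needed* can mean less than daily use, so a value below one is at least compatible with it. *As explained* carries no information on frequency. For those dispensations there is no prescribed dose to use, and 0.5 is an imputed value.

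The SAP itself says that such text is common. A difference between Tables 52 to 58 and the main tables could therefore come from prescribed doses that really differ from one per day, or from the constant. The planned output does not let a reader tell which. For hyponatraemia the question has a likely direction. Protocol section 9.7.2.1 reports a higher incidence in the first month of treatment, so adding later person-time tends to dilute the all-time rate and could be read as reassurance.

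**Working it through.** **Is there a figure to reproduce?** The 0.5 tablets per day has no derivation. The only other half-use figure is the 50% adherence behind the patient estimates (Protocol section 9.5.3, SAP section 3.1.2). Those reproduce with a 360-day year, which is inferred from the fit:

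- Germany: 661,950 / (360 × 0.5) = 3,677.5 (stated 3,678); × 0.18 = 661.9 (stated 662)
- Sweden: 117,250 / 180 = 651.4 (stated 651)
- Denmark: 82,260 / 180 = 457.0 (stated 457)

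The SAP does not cite this adherence assumption as the reason for the coding rule.

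**Per dispensation.** Days supplied = tablets / tablets per day, and 1 / 0.5 = 2. For 90 tablets, the supply illustrated in SAP section 9.1.1:

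- at 1 per day: 90 + gap 90 = 180 days
- at 0.5 per day: 180 + gap 180 = 360 days

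The factor of two also holds under the gap of twice the days supplied in Protocol section 9.3.1 (270 against 540 days).

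**Cohort supply.** If a share f of dispensed supply carries such text and all other texts say one per day, total days supplied rise by a factor 1 + f: 1.10 at 10%, 1.25 at 25%, 1.50 at 50%, 1.75 at 75%. The documents give no f.

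**Episode length with refills.** Four dispensations of 90 tablets, all affected, SAP gap, overlap carried forward, spacing assumed:

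| Spacing (days) | At 1 per day | At 0.5 per day | Ratio |
|---|---|---|---|
| 90 | 450 | 900 | 2.00 |
| 120 | 540 | 900 | 1.67 |
| 150 | 630 | 900 | 1.43 |
| 180 | 720 | 900 | 1.25 |
| 240 | 180 | 1,080 | 6.00 |

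In the last row the longer gap bridges dispensations that were separate before. Censoring limits the gain: with a 600-day cap the first row becomes 450 against 600 (1.33).

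**Effect on the all-time hyponatraemia rate.** Assumed rates: 60 per 1000 person-years in the first 30 days and 15 afterwards, one dispensation, person-time ending with treatment.

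- 90 tablets: (30×60 + 150×15)/180 = 22.5; (30×60 + 330×15)/360 = 18.75; change −17%
- 30 tablets: (30×60 + 30×15)/60 = 37.5; (30×60 + 90×15)/120 = 26.25; change −30%

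For a cohort with a share p of patients affected, 90 tablets: (4,050(1−p) + 6,750p) / (180(1−p) + 360p).

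- p = 0.25: 4,725/225 = 21.0 (−7%)
- p = 0.75: 6,075/315 = 19.3 (−14%)

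For 30 tablets: (2,250(1−p) + 3,150p) / (60(1−p) + 120p).

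- p = 0.25: 2,475/75 = 33.0 (−12%)
- p = 0.75: 2,925/105 = 27.9 (−26%)

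The true risk is unchanged throughout. In this example the first-month rate stays at 60 and the later rate at 15 under either coding; only the pooled row moves.

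**The case against.** The rule is openly prespecified, for a secondary run in a descriptive study without a hypothesis. Texts that state a dose are coded as written, so part of the run does test prescribed doses. *As needed* can mean less than daily use, and one per day is already the main analysis, so the two values can be said to bracket such texts. All of this stands. It does not justify giving *as explained* the same value, or leaving the share affected unreported.

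A reader might infer more than the documents support:

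- **That NOCDURNA exposure doubles.** This holds per affected dispensation. The cohort factor depends on an unknown share, and episode length can change by less or more than two.
- **That the run can move in one direction only.** A text prescribing more than one per day would shorten exposure, and longer windows also admit more events. For the companion shortened-gap run the SAP itself says that the effect on the rate cannot be predicted.
- **That all seven tables would look reassuring.** The early peak is documented for hyponatraemia only. Tables 55 to 58 cover mortality, MACE, VTE and heart failure. If Tables 52 to 58 follow the layout of Table 9, as Tables 45 to 51 do, separate first-month and later rows would show much of the dilution.
- **That the comparison with LUTS is biased.** Tables 52 to 58 are rate tables, and no IRR version of this run is listed. Any shift would arise from reading rates side by side.

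Finally, the effect needs person-time that ends with treatment. SAP section 5.1.3 also describes follow-up regardless of treatment status, under which the recoding would change nothing. However, SAP section 10.1.3 expects a shorter gap to reduce exposure time, which points to on-treatment time for these sensitivity runs.

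**Conclusion.** The point holds in a limited form. As written, the run mixes genuine prescribed doses with an unsupported constant, and the planned output does not separate the two. The doubling of days supplied and gap is exact for each affected dispensation; the effect on the cohort is not known.

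For pooled hyponatraemia, a fall of about 17% per affected patient (90 tablets) or 30% (30 tablets) is an illustration. It rests on the assumed rates, no refills and on-treatment person-time. At 25% to 75% of patients affected, the cohort figures are about −7% to −14% and −12% to −26% respectively. The documents do not support a claim about the other outcomes or about a planned treatment contrast. This is a small point about the interpretability of a sensitivity analysis. It does not touch the main analysis and says nothing about which dose is clinically right.

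**What to change.** In SAP section 10.1.3:

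1. Code explicit numeric instructions as written.
2. Give *as needed* and *as explained / no instruction* separate codes.
3. Report the number and share of dispensations in each category, including texts left uncoded.
4. Present Tables 52 to 58, where the data allow, with all non-specific texts kept at the main-analysis duration.
5. Add a second run with *as needed* at 0.5 per day, labelled as an assumption.

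The first run isolates the effect of stated doses; the second shows what the half-tablet assumption adds.

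Cost: one SAP paragraph, one extra category in the manual coding already planned, and one extra run of the tables. No new data are needed. The downside is that the first run may lie close to the main analysis if non-specific texts dominate. That would itself be informative, because it would show how little prescribed-dose information the registry holds.

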10.2 Secondary Safety Analyses

10.2.1 Secondary objective 1: Demographic and health characteristics

Demographic characteristics will be presented for both the Nocdurna \mathbb{R} and LUTS cohorts based on the index date. Other co-existing risk factors for primary and secondary outcomes of interest is also summarised. Characteristics will be described overall by cohort and stratified by sub-populations (elderly patients aged ≥ 65 years, patients with and without contraindications, patients with heart failure as used in section 10.2.7). The table shell is shown in Table 10 and will be repeated for the above sub-populations.

10.2.2 Secondary objective 2: Incidence of hyponatraemia requiring hospital intensive care

The analysis of hyponatraemia requiring hospital intensive care will be performed analogously to the analysis of incident events of symptomatic hyponatraemia (see 10.1.2). This analysis can only be done for Swedish data using the National Intensive Care Register from Värmland covering more than 90% of the Swedish intensive care units. ICU care for other reasons than hyponatraemia will not the included, while both primary and secondary diagnose codes for hyponatraemia will be counted.

10.2.3 Secondary objective 3: Incidence of clinically significant hyponatraemia

Analyses of incident and recurrent events of clinically significant hyponatraemia (<130 mmol/L) will be performed analogously to symptomatic hyponatraemia (see 10.1.2). Analyses will be performed among patients residing in the regions covered by the Danish National Laboratory Database Research Table. There will be 4 analysis stratified by the actual level of sodium concentrations where a *mild* hyponatraemia is a serum sodium concentration above 130 to less than 135 mmol/L, *moderate* is a serum sodium concentration of above 125 to less than 130 mmol/L, and *severe* is a serum sodium concentration of less than or equal to 125 mmol/L and the above specified as clinically significant hyponatraemia (<130 mmol/L)

The potential lack of serum sodium measurements, differences in the likelihood of being tested and intensity of testing will be addressed by describing the distribution of risk factors and background characteristics (e.g., relevant demographic and other risk factors such as comorbidities and co-medication) for tested and non-tested patients. The table shell for this analysis is shown in Table 12 and is repeating the baseline table, but only for the patients from 4 out of 5 Danish regions.

10.2.4 Secondary objective 4: All-cause mortality

The analysis of all-cause mortality will be performed analogously to that of incident events of symptomatic hyponatraemia, from the index date (see 10.1.2). Using a Poisson regression for mortality instead of a classical survival analysis make it possible to direct compare mortality with the other events rates in the study.

10.2.5 Secondary objective 5a: Incidence of major cardiovascular events

The analysis of incident MACE will be performed analogously to that of incident events of symptomatic hyponatraemia (see 10.1.2), from index date. Fatal and non-fatal MACE and VTE events will be assessed separately and this is possible in Denmark and Sweden.

In addition, time to events requiring hospital intensive care and cardiovascular death, respectively, will be described for patients with an incident diagnosis of MACE in the study time period. Events requiring hospital intensive care will be defined as a primary or secondary diagnosis of MACE recorded in a hospital intensive care unit (reported in Sweden only). Cardiovascular death is defined as a relevant diagnosis recorded as the underlying or contributing cause of death (reported for Sweden and Denmark). The description will be the analysis with number of subjects, mean (SD), median, range, interquartile range, and missing values as shown in Table 21 and Table 22 in Sweden and Denmark, respectively.

10.2.6 Secondary objective 5b: Incidence of major venous thromboembolic events

[figure not shown]
The analysis of incident VTE events will be performed analogously to that of incident events of symptomatic hyponatraemia (see 10.1.2), from index date.

[figure not shown]
Similar to MACE, time to events requiring hospital intensive care and death from a VTE event, respectively, will be described for patients with an incident diagnosis of VTE in the study time period. The description will be the analysis with number of subjects, mean (SD), median, range, interquartile range and missing values as shown in Table 25 and in Table 26 in Sweden and Denmark, respectively.

10.2.7 Secondary objective 6: Incidence of acute exacerbation of congestive heart failure

A new population will need to be established for this outcome, a population of patients with prevalent chronic heart failure (still divided in Nocdurna ® and LUTS). Prevalent chronic heart failure will be defined as ever having had a primary or secondary diagnosis of heart failure (ICD-10: I50) before the index date, but no recorded primary diagnosis of heart failure from hospital inpatient care or the acute and emergency ward in the 6 months prior to the index date (6 months

are programmed as 180 days). Among these patients, acute exacerbation of heart failure will be defined as a primary diagnosis of acute or acute-on chronic heart failure from hospital inpatient care or the acute and emergency ward, or death from heart failure as the underlying or contributory cause. It is obvious that this population will be much smaller than the original population. A new baseline table will also need to be established for these patients, as specified in Table 28.

The analysis itself of acute exacerbation of congestive heart failure will be performed analogously to that of incident events of symptomatic hyponatraemia (see 10.1.2).

10.2.8 Secondary objective 7: Comparative analyses

Where possible, for the comparative analyses of primary and secondary outcomes of interest, the same analyses (Poisson regression) as in Section 10.1.2 will be applied but now with treatment group (Nocdurna ®/LUTS) as an additional factor. Patients in the two groups will have their exposure time terminated when patients switch treatment (from Nocdurna to LUTS treatment or from LUTS treatment to Nocdurna). To investigate if the incidence rate ratio (IRR) for the Poisson regression of Nocdurna ® to LUTS depend on confounders, treatment by confounder interaction terms will be investigated to see if and to what extent the IRR depend on the respective confounding factor (age class and gender). A SAS macro have been developed for performing the analysis and is documented in 16.2. The output of the analysis is shown in Table 29. The analysis will show the percent change in the Nocdurna ® group as compared with the LUTS group (using the other variables as covariates), the percent change in the age class 65 to <= 75 year and above or equal 75 years as compared with the <65 year age class, and the percent change in the males as compared with the females. Also the 95% CI and the standard error of the means change are calculated, together with the p-value. The scale value for the model is calculated. The LUTS group is used as reference to ease the interpretation. Observe also that the Poisson regression is the same as the Section 10.1.2, but the output is changed to find the incidence rate ratios (IRR) instead of the incidence rates (IR) themselves. If the model does not converge/modelling assumptions are not met, only unadjusted rate ratios will be presented.

10.2.9 Secondary objective 8: Cardiovascular and thromboembolic events of interest resulting in treatment withdrawal

The analysis of this outcome will be performed analogous to that of incident events of symptomatic hyponatraemia in Section 10.1.2, but only for the Nocdurna ® patients. MACE and VTE events considered to be associated with treatment cessation will be those events for which the event date occurs within 14 days prior to the treatment cessation date. Serious MACE and VTE events will be defined as a primary or secondary diagnosis of MACE or VTE recorded in a hospital intensive care unit. This differs from the normal definition of serious adverse event. This can only be evaluated in Sweden.

The analysis will first calculate the treatment cessation date and then within a 14 days window before the treatment cessation date examine if there is a MACE or VTE event reported from the intensive care register.

Secondary objective 9: Incidence rate in patients stratified according to the label by proxy

The analysis of this outcome will be performed analogous to that of incident events of symptomatic hyponatraemia but only for the Nocdurna ® patients. The subgroup of patients adhering to the label will be defined by a proxy based on diagnosis and contra-indications as stated in the SmPC and the data for classifying the patients according to contraindications should be done as available in the respective registries.

Two population will be created for all Nocdurna ® patients, one with contra-indication for treatment and another as the remaining Nocdurna ® patients without contra-indication. The contra-indication for treatment must be present before the first recorded dispensation of Nocdurna ®.

The following diseases will be considered as contraindications for the prescription of Nocdurna ®, if the diseases are found before or at the index date.

- History of hyponatraemia
- Polydipsia
- Congestive heart failure (chronic)
- Kidney disease (chronic kidney disease stage 3 and over)
- Syndrome of inappropriate antidiuretic hormone secretion (SIADH)

The ICD 10 codes for the above can be found in the given in Table 71. The analysis will be done by using the SAS macro 'Nocdurna_mac' and changing the macro call with 'compare=Off label' and creating a class group with 'Off label' instead of 'LUTS' as described in section 16.1

The analysis of the sub-population will be done for the primary objective and for secondary objective 2, 3, 4, 5a, 5b and 6.

Observe that this analysis is changed from the description in the study protocol.

